## Scientific Background

Individuals with severe mental illnesses consume 35-44% of all cigarettes in the U.S., well above their representation in the population. This disproportionate level of smoking and limited access to cessation treatment has led to exceptionally high tobacco-related mortality and morbidity rates among smokers with schizophrenia. Of those who attempt cessation, relapse rates are much higher than found in the general population of smokers. Recent literature suggests that this discrepancy may be related to deficits in cognitive processes mediated by the prefrontal cortex (PFC). Specifically, impaired executive function and working memory have been directly linked to cessation failure among smokers with schizophrenia, and low cognitive control of impulsivity is strongly correlated with time to relapse in the general population. Moreover, schizophrenia is associated with persistent cognitive deficits, often linked to abnormal interaction among various brain regions, particularly right inferior frontal gyrus (IFG) and ventral striatum, making it difficult to cope with prepotent stimuli (e.g., smoking-related cues). Unfortunately, pharmacologic cessation treatments (e.g., Chantix, Wellbutrin) are only modestly effective in helping smokers with schizophrenia quit. To better assist this subset of highly vulnerable smokers achieve abstinence, development of new cessation adjuncts are needed. One promising route is the development of techniques that not only target underlying mechanisms that maintain smoking, but also specifically improve cognitive control.

Cognitive enhancement therapy increases cognitive performance in schizophrenia patients, particularly when working memory, processing speed, executive function, and social cognition are targeted. Standard protocols are intensive, taking 18 months to complete, making standard therapy a sub-optimal candidate for smoking cessation. However, the Cognitive Remediation (CR) component of cognitive enhancement therapy focuses specifically on cognitive training and is less intensive and lengthy. When combined with another cognition enhancement method, namely Transcranial Direct Current Stimulation (tDCS), CR may provide a robust and time efficient method of improving cognitive control among patients with schizophrenia. tDCS studies in our lab and others have demonstrated clear enhancement of attention, working memory, and risk aversion using this technique; as well as reductions in craving and amount of smoking. These findings, combined with knowledge of identified cognitive deficits in schizophrenia and the relationship between cognitive function and smoking cessation failure, suggest the potential of CR + tDCS to target cognitive deficits and smoking-related reactivity among smokers with schizophrenia. Specifically, we hypothesize that CR + tDCS will enhance cognitive control, reduce cue-induced craving and attenuate attentional bias (reaction time and ERPs) to smoking stimuli. Further, we will examine if these changes are associated with reductions in actual smoking behavior; and, we will explore the potential of CR + tDCS to increase quit intention and confidence in quitting among smokers with schizophrenia. Our specific aims are as follows:

## Study Objectives

**Aim 1:** Examine the effectiveness of CR + tDCS to improve behavioral and neurophysiological measures of **cognitive control** among smokers with schizophrenia. Using a 2 X 2 factorial design (n=20 per group) we will examine main and interactive effects of CR and tDCS on multiple measures of cognitive control. Hypothesis: Combined CR + tDCS will result in greater improvement in MATRICS measures of cognitive control, as well as continuous performance task (CPT) relative to the other groups (CR + sham tDCS, AC + tDCS, AC + sham tDCS).

**Aim 2:** Determine the effectiveness of CR + tDCS to attenuate **reactivity to smoking stimuli** among smokers with schizophrenia. Hypothesis: CR + tDCS will lead to greater reductions in cue-induced craving, and improved reaction time and ERP measures of attentional bias relative to the other groups (CR + sham tDCS, AC + tDCS, AC + sham tDCS).

**Aim 3:** Examine if cognitive control enhancement (Aim 1) and/or changes in reactivity to smoking-related stimuli (Aim 2) predict reductions in measures of **actual smoking behavior**. Hypothesis: Enhanced cognitive control and attenuation of reactivity to smoking stimuli will be directly

related to reductions in smoking topography (i.e., Latency to light, puff volume, and number of puffs) within the CR + tDCS group.

**Secondary Aim:** To inform future clinical research, we will also explore whether changes in cognitive control and smoking reactivity measures are associated with changes in **quit intention** and **confidence in quitting** from baseline assessment to end of study by training condition.

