## Study design and methods

Using a 2 x 2 design we examined CR (CR, active control [AC]) X tDCS (active, sham) to enhance cognitive control, reduce cue-induced craving, and attenuate attentional bias measures of reaction time and ERPs to smoking stimuli; and, we determined the impact of these changes on smoking behavior and intent to quit and confidence in quitting among daily smokers with schizophrenia. Participants were assigned to active (2.0 mA) CR + tDCS, CR + sham (0.1 mA) tDCS, active control (AC) + active tDCS, or AC + sham tDCS, each with anode electrode placement over the right inferior frontal gyrus (IFG) and cathode electrode placement over the left bicep. Similar to our previous studies participants received 30 minutes of either active or sham tDCS during each visit, starting at the beginning of the CR training. AC consisted of a self-paced knowledge- and vocabulary-based task in which participants were given sequential multiple-choice questions about factual information at a 6th-grade level. Participants underwent consecutive CR + tDCS sessions, 5 days a week, for 2 weeks. Cognitive control, cue-induced craving and attentional bias (reaction time & ERPs), as well as smoking topography were assessed during Week1 baseline testing and Assessment Week 4.

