## Procedures and protocol

Eligible participants will be invited to the Clinical Neurophysiology Research Lab for informed consent and further screening, including CO, Smoking and Medical history, PANSS, Intention to quit, Confidence in quitting, and hearing/vision testing to screen for sensory problems that may affect cognitive and/or EEG testing. After initial screening on Day 1, participants will be randomized. Randomization for the 4 groups will be stratified by current typical or atypical antipsychotic medication to control for the potential interaction of tDCS with medication class. A randomization assignment list will be generated for each category using a permuted 4 block design. Dropouts will be replaced. Participants will then be scheduled for two baseline testing sessions, completed the same week as initial screening. The first will utilize the MATRICS Clinical Consensus Battery (MCCB) for baseline testing of cognitive measures. Participants will perform form A of the MCCB at baseline, which includes composite scores for attention, processing speed, working memory, and reasoning/problem solving. Participants will also complete behavioral tests of cognitive control, cue reactivity and attentional bias during this visit. Participants will then complete a baseline EEG testing session on a separate visit in the same week. Electrophysiological measures of cognitive control will be examined using the 'AX'-type Continuous Performance Task (AX-CPT). Cue-induced craving and smoking topography will be assessed with a pictorial cue reactivity paradigm, and attentional bias will be measured using a modified stroop task. Following baseline testing (Week1), participants will return 5 days (M-F) for the next 2 weeks for cognitive training with CR / tDCS and will receive the same tDCS condition in each visit. In week 4, participants will perform follow-up testing using form B of the MCCB, behavioral tests of cognitive control, cue-reactivity, and attentional bias on the first day, and EEG testing on the second.

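### Aim 3 hypothesises its association within the CR + tDCS arm alone (about 20 of an implied 80), with no comparator for that association and no analysis specified for it

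*Combined protocol and SAP*

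**What the plan says.** Study Objectives states the Aim 3 hypothesis in one sentence. Better cognitive control and weaker responses to smoking cues are expected to be "related to reductions in smoking topography (i.e., Latency to light, puff volume, and number of puffs) within the CR + tDCS group". The objective sentence before it names no arm. It asks whether gains in cognitive control "and/or changes in reactivity to smoking-related stimuli (Aim 2) predict reductions in measures of" how participants really smoke.

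Aim 1 fixes the design: "Using a 2 X 2 factorial design (n=20 per group) we will examine main and interactive effects of CR and tDCS". Aims 1 and 2 both state their hypotheses "relative to the other groups (CR + sham tDCS, AC + tDCS, AC + sham tDCS"). Aim 3 names no comparison group. The Secondary Aim does look at associations across training conditions, but only for quit intention and confidence in quitting.

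Study design and methods describes cognitive control, craving, attentional bias and topography at Week 1 and Week 4, with no restriction by arm. Its overview says that "we determined the impact of these changes on smoking behavior and intent to quit and confidence in quitting among daily smokers with schizophrenia".

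Data Analysis specifies a 2x2 ANOVA of change, applied to every outcome, with a baseline-adjusted alternative. It mentions correlation only as a way of finding redundant outcomes. It gives no model for the Aim 3 association.

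**The concern.** The hypothesis is the only text that says in whom the Aim 3 association is to be examined. An analyst who follows it correlates two changes in a single treated arm. That has two consequences.

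- **Precision.** With about 20 participants only a very large correlation is detectable, and a null result would say almost nothing.
- **Interpretation.** Practice, day-to-day state or regression to the mean could make the two changes move together in any arm, including AC + sham tDCS. A correlation seen only in CR + tDCS cannot show whether the link differs from that in the controls, so it does not support the word *impact* in the design overview.

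The comparison data are to be collected anyway.

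**Working it through.** **The plan's own figure.** 4 groups x 20 = 80 (the total is implied, not stated), so CR + tDCS is 20/80 = 25%. The choice of 20 per group cannot be reproduced, because the documents give no significance level, power, effect size or SD.

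**Assumptions.** Two-sided 5%; 20 evaluable per arm (Procedures and protocol says dropouts are replaced but gives no attrition rate; "A randomization assignment list will be generated for each category using a permuted 4 block design", which with four groups implies equal allocation); true correlation r from 0.3 to 0.5; for the four-arm column, a similar within-arm slope in every arm.

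**Formulas.** Let m = n - 3 - k, where k is the number of arm terms.

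- Critical absolute r = t / sqrt(df + t²), with df = n - 2 - k.
- r detectable with 80% power = tanh((1.960 + 0.842)/sqrt(m)) = tanh(2.80/sqrt(m)).
- Power = Φ(atanh(r) x sqrt(m) - 1.960).
- 95% CI = tanh(atanh(r) ± 1.960/sqrt(m)).

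For CR + tDCS alone, n = 20, k = 0, df = 18 and m = 17. For all arms, n = 80, k = 3, df = 75 and m = 74.

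| Quantity | CR + tDCS alone | All four arms, arm terms |
|---|---|---|
| Critical absolute r | 0.444 | 0.224 |
| r for 80% power | tanh(2.80/√17) = 0.59 | tanh(2.80/√74) = 0.31 |
| Power at r = 0.3 | 25% | 76% |
| Power at r = 0.4 | 42% | 95% |
| Power at r = 0.5 | 62% | over 99% |
| 95% CI at observed r = 0.40 | -0.05 to 0.72 | 0.19 to 0.57 |

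Simulated t-tests at n = 20 gave 25% at r = 0.3 and 64% at r = 0.5, in line with the formula.

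**Does the association differ between CR + tDCS (20) and the other three arms combined (60)?** The standard error of the difference on the Fisher z scale is sqrt(1/17 + 1/57) = 0.276.

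- 0.5 against 0: 0.549/0.276 = 1.99; Φ(1.99 - 1.96) gives about 51% power.
- 0.5 against 0.2: (0.549 - 0.203)/0.276 = 1.25; Φ(1.25 - 1.96) gives about 24%.
- 80% power against 0 needs tanh(2.80 x 0.276) = 0.65.

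**What the arm terms do.** CR, tDCS and CR x tDCS use 3 degrees of freedom and fit the four arm means exactly. The pooled slope is therefore estimated wholly from differences between participants within arms. Its gain comes from sample size, not from randomised contrasts.

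**The case against.** The strongest reply is that the plan does not confine the analysis to one arm. One hypothesis clause does so, while the objective sentence, the background and the design overview name no arm. This stands: a reader might infer that the association is *tested* only in CR + tDCS, but no test is specified in any group. The supportable statement is that it is *hypothesised* there only.

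A reader might also infer that smoking topography has no control arm. The documents do not support that, because the ANOVA covers every outcome across all four arms. Only the association lacks a comparator.

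It is also fair to say that pooling has limits. The 95% power at r = 0.4 assumes a similar slope in every arm, AC + sham included. That is the very case in which the slope does not distinguish trained from untrained participants. The contrast that would distinguish them is weak, as shown above. Pooling also changes the question, since the sponsor asks about people given the combined training. These points stand as limits on the remedy. They do not defend an uncontrolled correlation in 20 participants, because a model with predictor-by-arm terms still reports the hypothesised slope.

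Finally, *impact* appears only in the overview; the aim and hypothesis use the language of prediction and relation. This makes the overstatement a matter of one phrase, which is easily corrected.

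**Conclusion.** The point holds in this limited form: the only Aim 3 hypothesis places the association in about a quarter of the implied sample, gives it no comparator, and has no analysis behind it. Followed as written, it needs a true correlation of about 0.59 for 80% power, against about 0.31 with all four arms. These figures rest on an assumed two-sided 5% level, 20 evaluable participants per arm and, for the four-arm figure, similar within-arm slopes.

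Two stronger readings should be resisted. Using all four arms does not recover the variation created by randomisation, because the arm terms remove it, so the pooled slope remains a non-randomised association. Nor is the restriction a defect that survives any choice of model, because a four-arm model with predictor-by-arm terms resolves it. The change is worth making because it is cheap and adds both precision and the missing comparison. It will not settle whether the link is specific to the combined training.

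**What to change.** In Aim 3 and Data Analysis:

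1. Define the analysis set as all randomised participants with Week 1 and Week 4 data.
2. For each topography measure, regress its change (or its Week 4 value given baseline; choose one in advance) on predictor change plus CR, tDCS and CR x tDCS. Report the pooled within-arm slope with a 95% CI.
3. Add predictor-by-arm terms. Report the hypothesised CR + tDCS slope and its difference from the other three arms, each with a 95% CI.
4. Describe the result as an association and replace *impact* in the overview.
5. State the limits: the pooled slope averages over arms and is not causal, and the arm-difference test has low power (about 51% for 0.5 against 0, 24% for 0.5 against 0.2), so a non-significant difference is not evidence of equal slopes.

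The cost is a reworded hypothesis and one paragraph, with no new data. The CR + tDCS slope will stay imprecise, since it still rests mainly on that arm's 20 participants. The design section is written in the past tense, so if results have already been seen, the four-arm analysis should be labelled as added later and shown beside the within-arm result.

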## Study design and methods

Using a 2 x 2 design we examined CR (CR, active control [AC]) X tDCS (active, sham) to enhance cognitive control, reduce cue-induced craving, and attenuate attentional bias measures of reaction time and ERPs to smoking stimuli; and, we determined the impact of these changes on smoking behavior and intent to quit and confidence in quitting among daily smokers with schizophrenia. Participants were assigned to active (2.0 mA) CR + tDCS, CR + sham (0.1 mA) tDCS, active control (AC) + active tDCS, or AC + sham tDCS, each with anode electrode placement over the right inferior frontal gyrus (IFG) and cathode electrode placement over the left bicep. Similar to our previous studies participants received 30 minutes of either active or sham tDCS during each visit, starting at the beginning of the CR training. AC consisted of a self-paced knowledge- and vocabulary-based task in which participants were given sequential multiple-choice questions about factual information at a 6th-grade level. Participants underwent consecutive CR + tDCS sessions, 5 days a week, for 2 weeks. Cognitive control, cue-induced craving and attentional bias (reaction time & ERPs), as well as smoking topography were assessed during Week1 baseline testing and Assessment Week 4.

## Procedures and protocol

Eligible participants will be invited to the Clinical Neurophysiology Research Lab for informed consent and further screening, including CO, Smoking and Medical history, PANSS, Intention to quit, Confidence in quitting, and hearing/vision testing to screen for sensory problems that may affect cognitive and/or EEG testing. After initial screening on Day 1, participants will be randomized. Randomization for the 4 groups will be stratified by current typical or atypical antipsychotic medication to control for the potential interaction of tDCS with medication class. A randomization assignment list will be generated for each category using a permuted 4 block design. Dropouts will be replaced. Participants will then be scheduled for two baseline testing sessions, completed the same week as initial screening. The first will utilize the MATRICS Clinical Consensus Battery (MCCB) for baseline testing of cognitive measures. Participants will perform form A of the MCCB at baseline, which includes composite scores for attention, processing speed, working memory, and reasoning/problem solving. Participants will also complete behavioral tests of cognitive control, cue reactivity and attentional bias during this visit. Participants will then complete a baseline EEG testing session on a separate visit in the same week. Electrophysiological measures of cognitive control will be examined using the 'AX'-type Continuous Performance Task (AX-CPT). Cue-induced craving and smoking topography will be assessed with a pictorial cue reactivity paradigm, and attentional bias will be measured using a modified stroop task. Following baseline testing (Week1), participants will return 5 days (M-F) for the next 2 weeks for cognitive training with CR / tDCS and will receive the same tDCS condition in each visit. In week 4, participants will perform follow-up testing using form B of the MCCB, behavioral tests of cognitive control, cue-reactivity, and attentional bias on the first day, and EEG testing on the second.

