## Eligibility Criteria

### Inclusion Criteria:

1. Between the ages of 18 & 65.
2. Currently meets DSM-5 criteria for Schizophrenia, Schizoaffective Disorder, Schizophreniform Disorder, or Delusional Disorder.
3. Ability to provide written informed consent
4. Smoke  $\geq$  7 cigarettes per day
5. Expired breath CO  $\geq$  10 ppm at screening
6. Stable medication regimen for  $\geq$  4 weeks (If on more than one psychotropic medication, main antipsychotic will be considered for stability)

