## Data Analysis

Prior to hypothesis testing, descriptive statistics and graphic displays will identify outliers and missing data and guide the use of transformations and appropriate tests. Correlation and principal component analysis will identify any outcomes reflecting the same underlying construct, and representative measures will be selected if necessary. We will use 2x2 ANOVA to assess the effects of tDCS (vs sham) and CR (vs AC) on pre-post change scores for all dependent variables. Should baseline differences be identified, post-training scores will be used as dependent variables, and baseline (pre-training) scores will be included as covariates in the analysis.

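### Antipsychotic class is a stratification factor, chosen because of a possible tDCS-by-class interaction, but neither planned model includes class or that interaction

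*Combined protocol and SAP*

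**What the plan says.** Under Procedures and protocol, randomisation to the four groups is "stratified by current typical or atypical antipsychotic medication to control for the potential interaction of tDCS with medication class". The method follows: "A randomization assignment list will be generated for each category using a permuted 4 block design".

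The Data Analysis section is the only analysis text supplied. Its main model is: "We will use 2x2 ANOVA to assess the effects of tDCS (vs sham) and CR (vs AC) on pre-post change scores". The fallback is conditional: "Should baseline differences be identified, post-training scores will be used as dependent variables", in which case "baseline (pre-training) scores will be included as covariates in the analysis". Neither sentence mentions medication class. Aim 1 under Study Objectives confines the interactions of interest to CR with tDCS, at 20 per group. No subgroup or sensitivity analysis by class appears elsewhere in the supplied text.

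**The concern.** The design and the analysis do not match in two ways.

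- **The stratum is not in the model.** Blocking within class makes the arm means less variable than an unadjusted model assumes. If class predicts the outcome, that variation stays in the residual, and the standard errors for tDCS, CR and their interaction come out too large. A stable class difference in level cancels out of a change score, so in the main ANOVA only a class difference in change matters. In the fallback, what matters is the class difference left after baseline.
- **The reason for stratifying is not followed through.** The stated worry is that tDCS may act differently by class, but no planned output would show it. Suppose the average tDCS effect is 0.6 SD, the interaction is 0.5 SD and the minority class is 20%. The effect is then 0.5 SD in the majority and 1.0 SD in the minority (0.8 × 0.5 + 0.2 × 1.0 = 0.6). The planned model reports only the 0.6, and so does a model with class as a main effect only. These figures are illustrative and do not come from the documents.

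**Working it through.** **Inputs from the documents.** Four groups of 20, so N = 80; two strata with permuted blocks of 4; a 2x2 model with interaction, so 80 − 4 = 76 residual df.

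**Assumed inputs.** The plan gives no alpha, power, effect size, SD or class mix, so its sample size cannot be reproduced. Assumed here: two-sided alpha 0.05; within-class SD = 1; tDCS main effect 0.6 SD; minority share *p* of 10, 20, 30 or 50%; class effect *d* on the analysed outcome of 0 to 0.8 SD.

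**Step 1: standard-error inflation.** With class balanced over the arms, omitting it adds 80·p(1−p)·d² to the expected residual sum of squares. Inflation = √[(76 + 80p(1−p)d²)/76] − 1. For p = 0.3, d = 0.8: 80 × 0.21 × 0.64 = 10.75, and √(86.75/76) − 1 = 6.8%.

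| Class effect | p = 10% | 20% | 30% | 50% |
|---|---|---|---|---|
| 0 SD | 0% | 0% | 0% | 0% |
| 0.3 SD | 0.4% | 0.8% | 1.0% | 1.2% |
| 0.5 SD | 1.2% | 2.1% | 2.7% | 3.2% |
| 0.8 SD | 3.0% | 5.3% | 6.8% | 8.1% |

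**Step 2: power.** The true standard error of the tDCS effect is √(1/40 + 1/40) = 0.224, so 0.6/0.224 = 2.68. With the stratum in the model, the critical value is 1.99 and power is about Φ(2.68 − 1.99) = 75.5% (76% in simulation). Without it, at p = 0.3 and d = 0.8, the effective critical value is 1.99 × 1.068 = 2.13. Power is then about Φ(2.68 − 2.13) = 71%, a loss of about 4.4 points.

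Simulation (10,000 trials per setting, same data analysed with and without the stratum, Monte Carlo error about 0.4 points) gave these losses:

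- no class effect: 0 points;
- 0.3 SD: 0.3 to 0.9 points;
- 0.5 SD: 0.8 to 2.2 points;
- 0.8 SD: 1.8 to 4.4 points for a 10 to 30% minority, and 5.1 at 50%.

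**Step 3: type I error without the stratum.** At p = 0.5 and d = 0.8 the effective critical value is 1.99 × 1.081 = 2.15, which gives about 3.5% on 76 df (simulated 3.4%). With no class effect the simulated rate was 4.9%. No setting showed an inflated error rate.

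**Step 4: what an interaction model could show.** With n₁ minority and n₀ majority participants, the interaction SE is √(4/n₁ + 4/n₀). The 95% half-width for the tDCS effect in the minority class is t(74) × √(4/n₁). For n₁ = 8 this is 1.99 × √0.5 = 1.41.

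| Minority n₁ / n₀ | Interaction SE (SD) | Power for 0.5 SD interaction | Minority half-width (SD) |
|---|---|---|---|
| 8 / 72 | 0.75 | 10% | ±1.41 |
| 16 / 64 | 0.56 | 14% | ±1.00 |
| 24 / 56 | 0.49 | 17% | ±0.81 |
| 40 / 40 | 0.45 | 20% | ±0.63 |

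The interaction detectable with 80% power is 2.12, 1.59, 1.39 and 1.27 SD for the same four splits.

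**The case against.** The case for leaving the plan alone has three parts.

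- **The loss is small.** It is zero if class does not predict the outcome and at most about 2 points up to 0.5 SD. The larger losses need an 0.8 SD class difference in change over a few weeks, which nothing in the documents supports. In the fallback model, baseline would absorb part of any stable class difference. All of this stands, and it limits the importance of the point. It is not a reason to omit a term that costs one degree of freedom.
- **The protocol never promised an interaction test.** No aim or hypothesis concerns class, and the randomisation sentence can be read as meaning only balance across arms. That is fair as far as it goes, but balance does not control an interaction, so the stated purpose remains unmet. The proposed term would be weak, as Step 4 shows. The interaction is therefore offered as an option and the stratum main effect is the core request.
- **Lack of bias is conditional.** It assumes that class balance survives into the analysed set. The simulations had no dropout, and the protocol says only "Dropouts will be replaced", with no rate and no rule for assigning replacements. This caveat stands.

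One further defence fails. The fallback's covariates are pre-training scores, the counterpart of the post-training scores. Medication class is not such a score, and the fallback applies only when baseline differences are found.

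**Conclusion.** The point holds. Class is used to randomise and then left out of both planned models, and the interaction given as the reason for stratifying is neither adjusted for nor estimated. The average treatment effects are not biased while class stays balanced, and any error in the tests is conservative. Over the range examined, the cost is 0 to 8.1% in standard error and 0 to about 5 points of power. The omission itself is certain from the text. Its size is not, because the class mix, the class effect and the tDCS effect are all assumed. It should be corrected because correction is almost free, not because the trial's validity depends on it.

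**What to change.** 1. Add the randomisation stratum, as used at randomisation, as a fixed factor in every treatment model: the 2x2 ANOVA and the fallback ANCOVA. In the ANOVA, residual df fall from 76 to 75. The data are already held for randomisation.
2. In the same text, state how the stratum is coded for a participant on both classes or neither. The Inclusion Criteria address multiple drugs only for stability ("If on more than one psychotropic medication, main antipsychotic will be considered for stability") and do not expressly require an antipsychotic. State also whether a replacement keeps the stratum and arm of the dropout. These are details needed to apply item 1, not separate findings.
3. Optionally, prespecify one model with a tDCS-by-class term, reporting the tDCS effect within each class with 95% intervals. Label it exploratory and imprecise, and do not read a non-significant interaction as evidence of a common effect.

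The cost is a few lines of SAP wording. Study design and methods is written partly in the past tense. If results have already been seen, the stratum-adjusted models should be reported as post hoc sensitivity analyses.

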## Interventions.

**Cognitive Remediation (CR).** CR incorporates a subset of components from Cognitive Enhancement Therapy found to have early benefits on the cognitive deficits of particular interest to the proposed studies and can be conducted more time-efficiently to achieve our specific goals. This abbreviated CR involves 20 hours of neurocognitive training using attention and processing speed training software developed by Ben-Yishay and colleagues. Deficits in Attention are addressed with exercises used to enhance vigilance and rapid decision making, inhibit irrelevant stimuli, and shift attention between auditory and visual modalities. These exercises facilitate reaction time in a temporal mode using auditory cues (The Attention Reaction Conditioner), spatial focusing with visual cues (the

Zero Accuracy Conditioner), and temporal vigilance with auditory and visual cues (Time Estimates). Our experience with over 200 patients with schizophrenia reveals that they successfully progress through these training exercises over the 20 hours of training. For the active control (AC) condition, participants will complete a self-paced knowledge- and vocabulary-based task of the same duration as CR to equate time spent on task, while omitting the cognitive control training aspect that is central to CR.

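### Participants are randomised before the main baseline tests, and fixed blocks of four could make up to a third of CR/AC allocations certain to a fully informed observer

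*Combined protocol and SAP*

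**What the plan says.** The Procedures and protocol section sets the order of steps. Screening covers CO, smoking and medical history, PANSS, intention to quit, confidence in quitting, and hearing and vision. Then: "After initial screening on Day 1, participants will be randomized". Only after that are two baseline sessions scheduled in the same week. The first holds the MCCB and the behavioural tests of cognitive control, cue reactivity and attentional bias; the second is EEG. Topography is recorded within the cue-reactivity paradigm. Training begins the following week.

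On the list, the same section says: "Randomization for the 4 groups will be stratified by current typical or atypical antipsychotic medication", and then "A randomization assignment list will be generated for each category using a permuted 4 block design". Study Objectives gives the arms and numbers: "Using a 2 X 2 factorial design (n=20 per group) we will examine main and interactive effects of CR and tDCS". One site is named: "Eligible participants will be invited to the Clinical Neurophysiology Research Lab for informed consent and further screening".

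The Interventions section describes CR: "This abbreviated CR involves 20 hours of neurocognitive training using attention and processing speed training software". The comparator is described in Study design and methods: "AC consisted of a self-paced knowledge- and vocabulary-based task in which participants were given sequential multiple-choice questions". Only the tDCS factor has a sham.

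Data Analysis applies a 2x2 ANOVA to pre-post change in all dependent variables. If baseline differences appear, it switches to post-training scores with baseline as a covariate.

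The available text does not say who holds the list, when an assignment is disclosed, whether block sizes vary, or whether testers or trainers are masked.

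**The concern.** There are two separate weaknesses.

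**Order of steps.** A baseline taken after allocation is protected only if nobody involved in the testing knows or can predict the arm. Here those baselines are half of each change score. They also decide whether the analysis switches to covariate adjustment, and they are then the covariate. A baseline shifted by knowledge of the arm could therefore affect the outcome, the choice of model and the adjustment.

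**Predictability.** In an open-task factor run in one laboratory, staff can learn past CR/AC assignments by seeing the sessions, without access to the list. With short fixed blocks, that knowledge can determine the next assignment. The risk is selective enrolment, or selective timing of enrolment, according to the expected task.

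**Working it through.** **Inputs.** Four arms, 20 per group, so 4 × 20 = 80 (Study Objectives). Two strata with one list each, and blocks of 4 (Procedures and protocol). With equal allocation each arm appears once per block, giving two CR and two AC places. The plan states no predictability figure, so there is none to reproduce.

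**Full knowledge of earlier CR/AC labels.** There are 6 equally likely CR/AC orders in a block.
- Chance that the next label is certain, positions 1 to 4: 0, 0, 1/3, 1. Position 3 is certain only if the first two match, which has probability 1/3. Share: (0 + 0 + 1/3 + 1)/4 = 1/3 = 33.3%.
- Best-guess success: (1/2 + 2/3 + 2/3 + 1)/4 = 70.8%, against 50% by chance.
- In a trial of 80 this is 80/3 = 26.7 allocations. Across the stratum splits tried from 80/0 to 41/39, allowing for incomplete last blocks, it is 25.3 to 26.7.

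**Delay before the task is visible.** Randomisation is in Week 1 and training starts the week after. The task cannot yet reveal the arm of someone randomised in the same stratum a few days earlier.
- Latest participant not visible: certain (0 + 0 + 0 + 1/3)/4 = 1/12 = 8.3%; best guess (1/2 + 1/2 + 2/3 + 2/3)/4 = 58.3%.
- Latest two not visible: certain 0%; best guess (1/2 + 1/2 + 1/2 + 2/3)/4 = 54.2%.

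The recruitment rate is not given, so the applicable row cannot be determined.

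| Observer's knowledge, fixed blocks of 4 | CR/AC certain | CR/AC best guess |
|---|---|---|
| All earlier labels in the stratum | 33.3% | 70.8% |
| All but the latest | 8.3% | 58.3% |
| All but the latest two | 0% | 54.2% |

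**Alternative block schemes, full knowledge of earlier labels.** For a fixed block of 2m with m places of each label, the certain share is 1/(m + 1): 1/3 for blocks of 4 and 1/5 for blocks of 8. The random schemes were simulated with 3,000 lists of 80. The observer was assumed to know the possible sizes but not their order, and to update exactly.

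| Scheme | Certain | Best guess |
|---|---|---|
| Fixed 4 | 33.3% | 70.8% |
| Fixed 8 | 20.0% | 66.6% |
| Random 4 or 8 | about 7.3% | about 67.9% |
| Random 4, 8 or 12 | about 2.7% | about 65.9% |

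Random sizes remove most of the certainty but little of the guessing advantage.

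**Which baselines are exposed.** Taken at screening, before allocation: PANSS, intention to quit, confidence in quitting. Taken after allocation: MCCB, behavioural cognitive control, cue-induced craving, topography, attentional bias and EEG measures.

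**The case against.** The strongest reply has four parts.

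1. **Being randomised on Day 1 is not the same as being told the arm on Day 1.** The protocol does not say that testers or participants learn the assignment before training. This stands. The exposure arises because disclosure is not described, not because it is shown to happen.

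2. **Many exposed measures leave a tester little room.** Cue reactivity is run by computer, Stroop reaction times are logged to the millisecond, topography comes from a CReSS holder, and ERPs are recorded. This reduces the likely size of any bias. It does not remove it: craving is self-rated, and performance tests depend on effort and on how they are administered.

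3. **Blocks equal to the number of arms are a recognised choice for a stratified trial of 80.** They protect balance by medication class, which is the stated purpose of stratifying. Eligibility also rests mainly on set criteria. Both points stand, but set criteria limit whom staff can enrol more than when they enrol them.

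4. **The one-third figure needs a very well-informed observer.** This stands too. The figure is a ceiling, and the delay before training can bring it down to zero.

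None of this answers the order of steps, which is explicit in the text and serves no stated purpose.

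**Conclusion.** The order of steps is the firmer part: randomisation precedes the baselines that feed most change scores, with no described masking of testers. The size of any resulting bias cannot be computed from the documents.

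The block-size part is a conditional exposure. For the CR/AC factor the certain share lies between 0% and 33%, and best-guess success between 54% and 71%, over the three states of knowledge examined. It rests on three inferences: the block size is fixed at 4, CR and AC are distinguishable to staff involved in enrolment, and those staff track each stratum. The protocol states none of these outright.

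A reader might infer more than the documents support:
- *A third of allocations are certain.* This is true only with full knowledge of earlier labels.
- *A third of four-arm allocations are certain.* If tDCS stays masked, no exact arm is certain. Naming the exact arm (1/4 + 1/3 + 1/2 + 1)/4 = 52.1% of the time would require knowing a sham-controlled factor, and nothing suggests it is visible.
- *Every change score is exposed.* Intention to quit and confidence in quitting are collected at screening, before allocation.
- *Bias occurred.* The text shows an opening for bias, not its use.

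**What to change.** 1. Release each assignment only after both Week 1 baseline sessions are complete. Training starts the following week, so this needs no extra visit. State who holds the list and that baseline testers do not know the arm.

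2. Generate each stratum's list with randomly ordered, undisclosed block sizes, for example 4 and 8.

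The cost is a new computer-generated list and a short protocol edit. The downside is slightly looser balance within a stratum when enrolment ends, mainly in the smaller one. An incomplete block of 4 leaves arms differing by at most 1; an incomplete block of 8, with two places per arm, can leave a difference of 2.

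The Study design and methods section is in the past tense. If enrolment is already finished, the list cannot be changed. The report should then give the block size used, who held the list, when assignments were disclosed, and whether baseline testers knew the arm.
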